6.14.5.1. Abnormal Hepatic Tests

Analyses for abnormal hepatic tests will involve 4 laboratory analytes: ALT, AST, total bilirubin, and ALP. In addition to the analyses described in Section 6.14.3, this section describes specific analyses for this topic.

First, the number and percentage of patients with the following abnormal elevations in hepatic laboratory tests at any time will be summarized between treatment groups:

- The percentages of patients with an ALT measurement $\geq 3\times$, $5\times$, and $10\times$ the central laboratory ULN during the treatment period will be summarized for all patients with a postbaseline value and for subsets based on various levels of baseline.
 - The analysis of $3\times$ ULN will contain 4 subsets: patients whose non-missing maximum baseline value is $\leq 1\times$ ULN, patients whose maximum baseline is $>1\times$ ULN but $<3\times$ ULN, patients whose maximum baseline value is $\geq 3\times$ ULN, and patients whose baseline values are missing.
 - The analysis of $5\times$ ULN will contain 5 subsets: patients whose non-missing maximum baseline value is $\leq 1\times$ ULN, patients whose maximum baseline is $>1\times$ ULN but $<3\times$ ULN, patients whose maximum baseline is $\geq 3\times$ ULN but $<5\times$ ULN, patients whose maximum baseline value is $\geq 5\times$ ULN, and patients whose baseline values are missing.
 - The analysis of $10\times$ ULN will contain 6 subsets: patients whose non-missing maximum baseline value is $\leq 1\times$ ULN, patients whose maximum baseline is $>1\times$ ULN but $<3\times$ ULN, patients whose maximum baseline is $\geq 3\times$ ULN but $<5\times$ ULN, patients whose maximum baseline is $\geq 5\times$ ULN but $<10\times$ ULN, patients whose maximum baseline value is $\geq 10\times$ ULN, and patients whose baseline values are missing.
- The percentages of patients with an AST measurement $\geq 3\times$, $5\times$, and $10\times$ the central laboratory ULN during the treatment period will be summarized for all patients with a postbaseline value and for subsets based on various levels of baseline. Analyses will be constructed as described above for ALT.

- The percentages of patients with a total bilirubin measurement $\geq 2 \times$ the central laboratory ULN during the treatment period will be summarized for all patients with a postbaseline value and subset into 4 subsets: patients whose non-missing maximum baseline value is $\leq 1 \times$ ULN, patients whose maximum baseline is $> 1 \times$ ULN but $< 2 \times$ ULN, patients whose maximum baseline value is $\geq 2 \times$ ULN, and patients whose baseline values are missing.
- The percentages of patients with an ALP measurement $\geq 1.5 \times$ the central laboratory ULN during the treatment period will be summarized for all patients with a postbaseline value and subset into 4 subsets: patients whose non-missing maximum baseline value is $\leq 1 \times$ ULN, patients whose maximum baseline is $> 1 \times$ ULN but $< 1.5 \times$ ULN, patients whose maximum baseline value is $\geq 1.5 \times$ ULN, and patients whose baseline values are missing.

Information collected from additional hepatic safety data collection forms will be provided in patient profiles.

Second, to further evaluate potential hepatotoxicity, an Evaluation of Drug-Induced Serious Hepatotoxicity (eDISH) plot will be created for all patients whether treated with baricitinib and/or other treatment using the whole study period(s). Each patient with at least 1 postbaseline ALT and total bilirubin will be included in the eDISH; therefore, a patient could contribute 1 or more points to the plot. The points correspond to maximum total bilirubin and maximum ALT, even if not obtained from the same blood draw. Scheduled and unscheduled measures will be used. Another eDISH plot will be provided where maximum AST is used in place of maximum ALT. A listing of patients potentially meeting Hy's rule will be provided (defined as $\geq 3 \times$ ULN for ALT or AST, and $\geq 2 \times$ ULN for total bilirubin, not necessarily at the same time).

When criteria are met for hepatic evaluation and completion of the hepatic safety CRF, investigators are required to answer a list of questions (see Compound level safety standards). A listing of the collected information will be generated together with a graphical patient profile. This includes demographics, disposition, and a display of study drug exposure, AEs, medications, and the liver-related measurements over time will be provided for these patients and any additional patients meeting ALT or AST measurement greater than or equal to $5 \times$ ULN (on a single measurement) or ALP measurement greater than or equal to $2 \times$ ULN (on a single measurement).

6.14.5.2. Hematologic Changes

Hematologic changes will be defined based on clinical laboratory assessments. Common Terminology Criteria for Adverse Events (CTCAEs) will be applied for selected laboratory tests and are described in the compound level safety standards. These CTCAE grading schemes are consistent with both Version 3.0 and Version 4.03 of the CTCAE guidelines (CTCAE 2003, 2010).

Treatment-emergent laboratory abnormalities occurring at any time during the treatment period and shift tables of baseline to maximum grade during the treatment period will be tabulated. Planned and unplanned measurements will be included. Treatment-emergence will be characterized using the following 5 criteria (as appropriate to the grading scheme):

- any increase in postbaseline CTCAE grade from worst baseline grade
- increase to Grade 1 or above at worst postbaseline
- increase to Grade 2 or above at worst postbaseline
- increase to Grade 3 or above at worst postbaseline
- increase to Grade 4 at worst postbaseline.

Shift tables will show the number and percentage of patients based on baseline to maximum during the treatment period, with baseline depicted by the most extreme grade during the baseline period. With each shift table, a shift table summary displaying the number and percentage of patients with maximum postbaseline results will be presented by treatment group for each treatment period within the following categories:

- Decreased: postbaseline category < baseline category,
- Increased: postbaseline category > baseline category,
- Same: postbaseline category = baseline category.

A laboratory-based treatment-emergent outcome related to increased platelet count will be summarized in similar fashion. Treatment-emergent thrombocytosis as a laboratory-based abnormality will be defined as an increase in platelet count from a maximum baseline value ≤ 600 billion/L to any postbaseline value > 600 billion/L (Lengfelder et al. 1998). Planned and unplanned measurements will be included.

A listing of patients with treatment-emergent thrombocytosis may be provided for safety review.

6.14.5.3. Lipids Effects

Lipids effects will be assessed through analysis of elevated total cholesterol, elevated LDL cholesterol, decreased HDL cholesterol, and elevated triglycerides as described in Section 6.14.3 and with TEAEs potentially related to hyperlipidemia.

Categorical analyses will be performed using National Cholesterol Education Program (NCEP) Adult Treatment Panel (ATP) III guidelines (2002) as shown in the compound level safety standards. The grade-like categories shown in this table are ordered from traditionally most desirable to least desirable for the purposes of these analyses.

Shift tables will show the number and percentage of patients based on baseline to the least desirable category during the treatment period, with baseline depicted by the least desirable category during the baseline period. With each shift table, a shift table summary displaying the number and percentage of patients with the least desirable postbaseline results will be presented by treatment group for each treatment period within the following categories:

- Decreased: postbaseline category more desirable than baseline category,
- Increased: postbaseline category less desirable than baseline category,
- Same: postbaseline category = baseline category.

Treatment-emergent laboratory abnormalities related to elevated total cholesterol, elevated triglycerides, elevated LDL cholesterol, and decreased and increased HDL cholesterol occurring

at any time during the treatment period will be tabulated using the NCEP categories shown in the compound level safety standards.

Treatment-emergent elevated total cholesterol will be characterized as follows:

- increase to categories ‘Borderline high’ or ‘High’
- increase to category ‘High.’

Treatment-emergent elevated triglycerides will be characterized as

- increase to categories ‘Borderline high,’ ‘High,’ or ‘Very high’
- increase to categories ‘High’ or ‘Very high’
- increase to category ‘Very high.’

Treatment-emergent elevated LDL cholesterol will be characterized as

- increase to categories ‘Borderline high,’ ‘High,’ or ‘Very high’
- increase to categories ‘High’ or ‘Very high’
- increase to ‘Very high.’

Treatment-emergent abnormal HDL cholesterol will be characterized as

- decreased
 - decrease to categories ‘Normal’ or ‘Low’
 - decrease to category ‘Low’
- increased
 - increase to categories ‘Normal’ or ‘High’
 - increase to category ‘High’.

The percentages of patients with treatment-emergent potential hyperlipidemia will be summarize by treatment, ordered by decreasing frequency in the baricitinib 4-mg group using a predefined MedDRA list of PTs that is a subset of the narrow scope PTs in the MedDRA SMQ ‘Dyslipidemia’ (code 200000026) [see Compound level safety standards].

6.14.5.4. Renal Function Effects

Effects on renal function will be assessed through analysis of elevated creatinine.

Common Terminology Criteria for Adverse Events will be applied for laboratory tests related to renal effects as shown in the compound level safety standards. This CTCAE grading scheme is consistent with both Version 3.0 and Version 4.03 of the CTCAE guidelines. Shift tables will show the number and percentage of patients based on baseline to maximum during the treatment period, with baseline depicted by highest grade during the baseline period. Treatment-emergent laboratory abnormalities related to elevated creatinine occurring at any time during the treatment period will be tabulated. Refer to the Compound level safety standards for details.

6.14.5.5. Elevations in Creatine Phosphokinase (CPK)

Elevations in creatine phosphokinase (CPK) will be addressed using CTCAE criteria as shown in the compound level safety standards. This CTCAE grading scheme is consistent with both Version 3.0 and Version 4.03 of the CTCAE guidelines. Analyses will be the same as the

CTCAE analyses specified for laboratory tests related to renal function events in Section [6.14.5.2](#).

A listing of elevated CPK (CTCAE grade of 3 or above) will be provided for medical safety review.

Treatment-emergent adverse events potentially related to muscle symptoms may be analyzed, based on reported AEs. The Muscle Symptoms special search category is a pre-defined MedDRA search criteria list that contains the narrow scope terms from the Rhabdomyolysis / myopathy SMQ (code 20000002) plus selected terms from the Musculoskeletal SOC. These terms are shown in the compound level safety standards.

6.14.5.6. Infections

Infections will be defined using all the PTs from the Infections and Infestations SOC as defined in MedDRA. Serious infection will be defined as all the infections that meet the SAE criteria.

The number and percentage of patients with TEAEs of infections, serious infections, and infections resulting in permanent study drug discontinuation will be summarized by treatment group using MedDRA PTs. The proportion of patients developing skin infections requiring antibiotic treatment by Week 16 will also be summarized on the overview of infections table.

The number and percentage of patients with TEAEs of infections by maximum severity will be summarized by treatment group using MedDRA PTs.

Treatment-emergent infections will be reviewed in context of other clinical and laboratory parameters via a listing (details see Compound level safety standards).

The TEAE infections will be further analyzed in terms of potential opportunistic infection, herpes zoster and herpes simplex. Summary of HBV DNA monitoring results and association between infection and neutropenia/lymphopenia will also be provided in the context of infections.

Opportunistic infection

To identify potential opportunistic infections (POIs), the following approach will be used:

- identifying the POIs using a list of MedDRA PTs (refer to the compound level safety standards).

Potential opportunistic infections is identified through these search approaches and may be combined in one list for medical assessment and final classification of whether the case met the modified Winthrop definitions for OI.

A final listing for OIs will be provided for the CSR and to assist the composition of patient narratives.

Herpes zoster

Cases of herpes zoster will be further classified as follows:

- localized or non-multidermatomal-involvement of the primary and/or adjacent dermatomes only
 - complicated – documented ocular (cornea or deeper structure; for example, iritis, keratitis, retinitis, etc.) or motor nerve involvement (e.g., palsy; post herpetic neuralgia [PHN] does not meet criteria for motor nerve involvement).
 - uncomplicated-localized or non-multidermatomal cases that are not complicated
- multidermatomal-involvement beyond primary and adjacent dermatomes (that is, >3 contiguous dermatomes) or involvement of two or more non-contiguous dermatomes
 - complicated-documented ocular (cornea or deeper structure; for example iritis, keratitis, retinitis, etc.) or motor nerve involvement
 - uncomplicated-multidermatomal cases that are not complicated
- disseminated-systemic infection, widespread, often bilateral with or without internal organ involvement (i.e., visceral involvement) and other systemic signs/symptoms.
- Recurrent - >1 infection occurring in an individual patient during the course of participation in the baricitinib clinical program.

All herpes zoster will undergo medical review to determine the classification as described above.

A summary of herpes zoster table will be provided. The summary table will also include event maximum severity, seriousness, whether resulting in temporary study drug interruption, whether resulting in study drug discontinuation, whether treated with antiviral medication, and event outcome. The incidence rate adjusted for observation time will also be provided (as defined in Section 6.14.2). Of note, in the context of herpes zoster, antiviral medication treatment is defined as that the medication was initiated at the event start date, or within 30 days before or after the event start date. The antiviral medication for herpes zoster includes but not limited to Aciclovir, Brivudine, Cidofovir, Famciclovir, Foscarnet, Ganciclovir, Penciclovir, Valaciclovir, Valganciclovir, Vidarabine (best presented by J05AB, J05AC, J05AE, and J05AH ATC codes). For specific data lock, medical representatives will review the concomitant medication list and make adjustment of the above list if necessary.

If a patient has more than 1 event of herpes zoster, the event with the maximum severity will be used in these summary tables. If more than 1 event of herpes zoster occurs with the same severity, the event with the longest duration will be used in the summary table.

Herpes simplex

A summary analysis of herpes simplex will be provided. Herpes simplex will be defined based on MedDRA preferred term as listed in the compound level safety standards (both narrow and broad terms in the herpes simplex section). The list needs to be reviewed by GPS/medical prior to data locks (final and interim). The summary table will also include event maximum severity, seriousness, whether resulting in temporary study drug interruption, whether resulting in study

drug discontinuation, and whether treated with antiviral medication. The exposure-adjusted incidence rate (EAIR) will also be provided.

If a patient has more than 1 event of herpes simplex, the event with the maximum severity will be used in these summary tables. If more than 1 event of herpes simplex occurs with the same severity, the event with the longest duration will be used in the summary table.

Skin Infections

A summary analysis of skin infections will be provided. Skin infections will be defined based on MedDRA preferred term as listed in Compound level safety standards.

HBV DNA

A listing of patients with detectable hepatitis B virus (HBV) deoxyribonucleic acid (DNA) post baseline will be provided.

HBV DNA status post baseline (not detectable, detectable but not quantifiable [i.e., LLOD], quantifiable [i.e., LLOD]) will be summarized by treatment group stratified by baseline HBV serology status, specifically:

- HBsAb+ / HBcAb+
- HBsAb- / HBcAb+

Association between infection and neutropenia/lymphopenia

To evaluate the association between infection and neutropenia, for the controlled analysis sets, the frequency of infections will be provided by patient subgroups defined by the worst CTCAE grades of neutropenia during the analysis period, respectively. Infection outcomes considered for this analysis are any treatment-emergent infection, serious infection and herpes zoster. For this analysis, no statistical comparison will be provided.

In addition, and depending on the number of cases with CTCAE Grade 2 or greater, a summary table will be provided for treatment-emergent infections that were preceded or accompanied by neutropenia. For this analysis, neutropenia is defined as (1) CTCAE Grade 2 or greater, (2) Grade 3 or greater. Infection events with onset date ≤ 14 days before or after the Grade 2 neutrophil count collection date will be considered as infections preceded or accompanied by neutropenia.

Similar analyses as above will be conducted to evaluate the association between infection and lymphopenia.

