6.14.2. Adverse Events

Adverse events are recorded in the eCRFs. Each AE will be coded to system organ class (SOC) and PT using the Medical Dictionary for Regulatory Activities (MedDRA) version that is current at the time of database lock. Severity of AEs is recorded as mild, moderate, or severe.

A TEAE is defined as an event that either first occurred or worsened in severity after the first dose of study treatment and on or prior to the last visit date during the analysis period. The analysis period is defined as the treatment period plus 30 days off-drug follow-up time.

Adverse events are classified based upon the MedDRA PT. The MedDRA Lowest Level Term (LLT) will be used in defining which events are treatment-emergent. The maximum severity for each LLT during the baseline period up to first dose of the study medication will be used as baseline. If an event with missing severity is preexisting during the baseline period, and persists during the treatment period, then the baseline severity will be considered mild for determining treatment-emergence (that is, the event is treatment-emergent if the severity is moderate or severe postbaseline and not treatment-emergent if the severity is mild postbaseline). If an event occurring postbaseline has a missing severity, then the event is considered treatment-emergent unless the baseline is severe, in which case the event is not treatment-emergent. The day and time for events where onset is on the day of the first dose of study treatment will both be used to distinguish between pretreatment and posttreatment to derive treatment-emergence. Should there be insufficient data for AE start date to make this comparison (for example, the AE start year is the same as the treatment start year, but the AE start month and day are missing), the AE will be considered treatment-emergent.

In general, summaries will include the number of patients in the safety population (N), frequency of patients experiencing the event (n), and relative frequency (that is, percentage; $n/N * 100$). For any events that are gender-specific based on the displayed PT, the denominator used to compute the percentage will only include patients from the appropriate gender.

For events of special interest, a more robust incidence rate, IR per 100 patient-years of observation (PYO) may be provided. Patient-years of observation will be calculated as the sum

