6.14.2.2. Serious Adverse Event Analyses

Consistent with the International Conference on Harmonisation (ICH) E2A guideline (1994) and 21 Code of Federal Regulations (CFR) 312.32 (a) (2010), a SAE is any AE that results in any one of the following outcomes:

- Death
- Initial or prolonged inpatient hospitalization
- A life-threatening experience (that is, immediate risk of dying)
- Persistent or significant disability/incapacity
- Congenital anomaly/birth defect

The number and percentage of patients who experienced any SAE will be summarized by treatment using MedDRA PT nested within SOC. Events will be ordered by decreasing frequency in the baricitinib 4-mg group within decreasing frequency in SOC. The SAEs will also be summarized by treatment using MedDRA PT without SOC.

An individual listing of all SAEs will be provided. A listing of deaths, regardless of when they occurred during the study, will also be provided.

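### The dedicated herpes zoster and simplex tables take every row from the patient's most severe event, so their seriousness, interruption, discontinuation and antiviral counts can be too low

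*SAP*

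**What the plan says.** SAP Section 6.14.5.6 plans a dedicated table for herpes zoster and another for herpes simplex. For both, "The summary table will also include event maximum severity, seriousness, whether resulting in temporary study drug interruption, whether resulting in study drug discontinuation". Antiviral treatment is a further row in both, and event outcome is a further row for zoster only.

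The section then says how to treat repeat events. For zoster: "If a patient has more than 1 event of herpes zoster, the event with the maximum severity will be used in these summary tables". For simplex: "If a patient has more than 1 event of herpes simplex, the event with the maximum severity will be used in these summary tables". In both, when severity is equal, "the event with the longest duration will be used in the summary table".

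Two definitions elsewhere in the SAP bear on this. Section 6.14.2 states: "Severity of AEs is recorded as mild, moderate, or severe". Section 6.14.2.2 defines seriousness by consequence: "a SAE is any AE that results in any one of the following outcomes". Section 6.14.5.6 carries that over to infections: "Serious infection will be defined as all the infections that meet the SAE criteria".

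**The concern.** The rule picks one event per patient on severity, then on duration. That event supplies all the rows, including several that are neither severity nor duration. Whether an event was serious, interrupted or stopped study drug, or was treated with an antiviral is a separate fact about it. The most severe event need not be the one with these consequences.

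A reader of a row on drug discontinuation in a herpes table will take it as the number of patients in whom a herpes event stopped study drug. Under the written rule it is the number whose most severe herpes event did so. The second number can be smaller, and the SAP plans no label that tells the reader which is shown. What is at stake is the accuracy of these two special-topic tables and their agreement with the other safety displays. No efficacy result, alpha allocation or power figure depends on it.

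**Working it through.** The SAP states no figure that depends on this rule, so there is nothing to reproduce. The check applies the rule as written.

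**1. Does the rule govern all rows?** The text refers to the tables as a whole and exempts no row. The duration tie-break supports this reading. If the rule served only the severity row, no tie-break would be needed, because events of equal severity give the same entry. A tie-break matters only if the chosen event also supplies other attributes.

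**2. Two illustrative patients** (constructed, not from the SAP):

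| Patient | Event A | Event B | Event selected | Table shows |
|---|---|---|---|---|
| 1 | Severe, non-serious, no drug action | Moderate, hospitalised, study drug stopped | A (more severe) | Not serious, not discontinued |
| 2 | Moderate, non-serious, longer | Moderate, serious, shorter | A (tie, longer) | Not serious |

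Both patients had a serious herpes event, and neither is counted as serious in the herpes table.

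**3. Direction.** For patient i, let X_ij = 1 if event j has a given attribute and 0 otherwise, and let s be the selected event.
- Written rule: Y_i = X_is
- Any-event rule: Z_i = max over j of X_ij

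Since X_is is one of the X_ij, Y_i ≤ Z_i for every patient. Each arm's count under the written rule is therefore at or below the any-event count. This applies to seriousness, interruption, discontinuation and antiviral treatment. It does not apply to the severity row, where the maximum is what is wanted.

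**4. Size per affected patient.** Planned arm sizes are in SAP Section 5.1.
- Baricitinib arm: 1/120 = 0.83 percentage points
- Placebo arm: 1/240 = 0.42 percentage points

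The SAP gives no frequency of repeat herpes events, so the number of affected patients cannot be computed. Three conditions must hold together:
- the patient has two or more events of the same type;
- the events differ on the attribute;
- the event with the attribute is the less severe one or, at equal severity, the shorter one.

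**5. Comparison with the other displays.** Section 6.14.5.6 also plans this: "The number and percentage of patients with TEAEs of infections, serious infections, and infections resulting in permanent study drug discontinuation will be summarized". That display carries no one-event rule. Section 6.14.2.2 plans SAE summaries by preferred term and a full SAE listing. Section 6.14.2.3 does the same for permanent discontinuations and for interruptions because of adverse events, again with listings. Patient 1 therefore counts as serious and discontinued in those displays, and as neither in the herpes table.

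**6. Incidence rate for zoster.** Section 6.14.5.6 takes the zoster rate from Section 6.14.2, where a patient's observation time stops at the event date. Neither section says which event is meant when there are several. To gauge the effect, suppose a later event were used, 8 weeks after the first:
- Extra time: 8 × 7 = 56 days; 56/365.25 = 0.153 patient-years
- Arm total, assuming 120 patients with 112 days each: 120 × 112/365.25 = 36.8 patient-years
- Shift in the denominator: 0.153/36.8 = 0.4% per affected patient

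**The case against.** The strongest reply is that little is lost. Serious and drug-stopping herpes events still appear by treatment group and preferred term in the serious-infection, SAE, discontinuation and interruption outputs. Zoster cases also go to medical review, and recurrent cases have their own class. This stands. It confines the loss to the two herpes tables. A reader might infer from the undercount that the rule could hide a dose-related harm, but these displays mean that the SAP does not support that reading. Nor does it contain recurrence data to show that one arm would be affected more than another.

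The reply does not dispose of the point. The other summaries are organised by preferred term, whereas herpes simplex is defined by a list of narrow and broad terms. The dedicated table is where the SAP plans a pooled simplex count with these attributes, and a reader would have to rebuild that count from listings.

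A second reply is that the rule is deterministic and describes each patient by one real event, which keeps severity, outcome and drug action together. That is a legitimate design for a profile of the worst event. However, the SAP does not label the rows that way, and without a label they read as patient-level counts.

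A third caution concerns the incidence rate. A reader might infer that the maximum-severity rule also inflates time at risk. Nothing in the SAP says that the rule replaces the event date in the Section 6.14.2 formula. Moreover, that formula is invoked for zoster only; simplex has an exposure-adjusted rate that is not tied to it. This is an ambiguity, not an error.

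**Conclusion.** The point holds for the two dedicated herpes tables. As written, the rule can only understate the number of patients with any herpes event that was serious, interrupted or stopped study drug, or was treated with an antiviral. It can also make these tables disagree with other displays in the same report.

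The size is 0.83 percentage points per affected patient in a baricitinib arm and 0.42 in placebo, on the planned arm sizes; safety-population denominators may differ slightly. The number affected is unknown. It is probably small, given 16 weeks of treatment plus up to 30 days of follow-up and the need for repeat events with differing attributes. The zoster rate ambiguity is worth about 0.4% of an arm's patient-years per affected patient, under the 56-day and full-112-day assumptions.

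The conclusion rests on reading the rule as covering every row, which the wording and the tie-break both support. It is worth correcting because the remedy costs almost nothing, and not because a safety signal would otherwise be lost.

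**What to change.** In Section 6.14.5.6, for both herpes zoster and herpes simplex:

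- Take the severity row as the maximum over all of the patient's events.
- Derive seriousness, temporary interruption, permanent discontinuation and antiviral treatment per patient as yes if any event has the attribute.
- Keep the single-event rule, with its tie-break, only for descriptors that need one event, such as zoster outcome, and label that row as describing the most severe event.
- State that the zoster incidence rate stops a patient's observation time at the first event.

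If the sponsor prefers to keep one event per patient throughout, a footnote saying that all rows describe the most severe event would explain any disagreement with the other displays. It would not supply the any-event counts.

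The cost is a few sentences of SAP text and minor programming. No new data are needed.
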